## 7 ADVERSE EVENT REPORTING

### 7.1 DEFINITIONS

**Adverse Event (AE):** any untoward medical occurrence in a patient or clinical trial subject administered a medicinal product and which does not necessarily have a causal relationship with this treatment. *An AE can therefore be any unfavourable and unintended sign (including an abnormal laboratory finding), symptom, or disease temporally associated with the use of an investigational medicinal product (IMP), whether or not considered related to the IMP.*

An adverse event will be followed until it resolves or until 30 days after a participant terminates from the study, whichever comes first.

**Adverse Reaction (AR):** all untoward and unintended responses to an IMP related to any dose administered. *All AEs judged by either the reporting investigator or the sponsor as having reasonable causal relationship to a medicinal product qualify as adverse reactions. The expression reasonable causal relationship means to convey in general that there is evidence or argument to suggest a causal relationship.*

**Unexpected Adverse Reaction:** an AR, the nature or severity of which is not consistent with the applicable product information (eg investigator's brochure for an unapproved investigational product or summary of product characteristics (SmPC) for an authorised product). *When the outcome of the adverse reaction is not consistent with the applicable product information this adverse reaction should be considered as unexpected. Side effects documented in the SmPC which occur in a more severe form than anticipated are also considered to be unexpected.*

**Serious Adverse Event (SAE) or Serious Adverse Reaction:** any untoward medical occurrence or effect that:

- **Results in death**
- **Is life-threatening** – *refers to an event in which the subject was at risk of death at the time of the event; it does not refer to an event which hypothetically might have caused death if it were more severe*
- **Requires hospitalisation, or prolongation of existing inpatients' hospitalisation**
- **Results in persistent or significant disability or incapacity**
- **Is a congenital anomaly or birth defect**

Medical judgement should be exercised in deciding whether an AE/AR is serious in other situations. Important AE/ARs that are not immediately life-threatening or do not result in death or hospitalisation but may jeopardise the subject or may require intervention to prevent one of the other outcomes listed in the definition above, should also be considered serious.

**Suspected Unexpected Serious Adverse Reaction (SUSAR):** any suspected adverse reaction related to an IMP that is both unexpected and serious.

**Any symptoms requiring treatment for anaphylaxis** (adrenaline, steroids, salbutamol) **will be classified as a SERIOUS ADVERSE REACTION** and must be documented on both the CRF as well as through completion of a SAE form. The investigator should also make a notification to the MHRA should also be made through the yellow card scheme (<https://yellowcard.mhra.gov.uk/>).

For the purpose of this study, SARs and SAEs not related to asthma/wheezing will only be collected where onset is within 72 hours of vaccine administration. Those relating to respiratory symptoms will be collected up to one month after LAIV at visit 1.

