## PROTOCOL SYNOPSIS

Title	Safety of Nasal Influenza Immunisation in Children with Asthma
Abbreviated title	SNIFFLE 4 study
Eudra CT registration no.	2016-002352-24
HRA NREC Number	16/WM/0276
Sponsor R&D Number	16SM3348
Clinicaltrials.gov registration no.	NCT02866942
HRA IRAS / UKCRN reference	207822
Primary objective	To assess changes in asthma symptoms / symptom control following LAIV in children with asthma / recurrent wheezing, including children with difficult/severe asthma.
Intervention and key procedures	Single dose of intranasal LAIV  (To fulfil a duty of care, influenza vaccine-naïve individuals under 9 years of age AND at high risk for severe influenza infection will be eligible for a second dose 4 weeks later, as per DoH guidelines).  Nasal swab (collected by parent) in the event of flu like illness from January 2017 until end of Influenza season (approx. April 2017)
Safety	Participants will be immunised in the hospital environment, by personnel qualified in the recognition and treatment of anaphylaxis, and observed for at least 20 minutes following a dose.  Families will be contacted at 72 hours after immunisation to establish the occurrence of any delayed effects.  Completion of validated questionnaire at 4 weeks after LAIV.
Patient group	Children and young people with asthma / recurrent wheezing attending paediatric outpatients, aged 2-18 years old (inclusive). Target recruitment of 840 subjects.
Primary outcome	Change in asthma symptoms and control pre and 4 weeks post LAIV, as assessed by validated questionnaire: 
 
• Age 2-4 years: TRACK questionnaire
 
• Age 5-11 years: C-ACT score
 
• Age 12+ years: ACT score
 

Secondary outcomes	
 
1. Incidence of adverse events (AEs) and serious adverse events (SAEs) following LAIV
 
2. To document influenza virus shedding in the week following vaccination with LAIV
 

Sponsor	Imperial College Healthcare NHS Trust
Funding	Department of Health Policy Research Programme (NVEC039/0031)

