### 6.1.2 SECOND DOSE OF LAIV

Children who meet DoH criteria for specified 'clinical risk categories' (Table 1) and are under 9 years of age and have not received prior seasonal influenza vaccination will be offered a second dose of LAIV at least 4 weeks later. We expect very few children to meet this criteria, as most would have received prior influenza vaccination (in SNIFFLE 1, no child would have required a second dose). However, there is a duty of care to our participants and we are therefore including provision for a second dose in this protocol.

Data pertaining to second visits will be collected on a separate CRF, but not used in the primary analysis.

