**Table 1: Clinical risk categories requiring a second dose of LAIV in vaccine-naïve children under age 9 yrs:**

Chronic respiratory disease	
 
• Asthma requiring continuous or repeated use of inhaled or systemic steroids or with previous exacerbations requiring hospital admission.
 
• Chronic obstructive pulmonary disease (COPD) including chronic bronchitis and emphysema; bronchiectasis, cystic fibrosis, interstitial lung fibrosis, pneumoconiosis and bronchopulmonary dysplasia (BPD).
 
• Children who have previously been admitted to hospital for lower respiratory tract disease.
 

Chronic heart disease	Congenital heart disease, hypertension with cardiac complications, chronic heart failure.
Chronic kidney disease	Chronic kidney disease at stage 3, 4 or 5, chronic kidney failure, nephrotic syndrome, kidney transplantation.
Chronic liver disease	Cirrhosis, biliary atresia, chronic hepatitis
Chronic neurological disease	Stroke, transient ischaemic attack (TIA). Conditions in which respiratory function may be compromised due to neurological disease (e.g. polio syndrome sufferers). Clinicians should consider on an individual basis the clinical needs of patients including individuals with cerebral palsy, multiple sclerosis and related or similar conditions; or hereditary and degenerative disease of the nervous system or muscles; or severe neurological or severe learning disability.
Diabetes	Type 1 diabetes, type 2 diabetes requiring insulin or oral hypoglycaemic drugs, diet controlled diabetes.

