### 8.4.2 LABELLING, DESPATCH, AND STORAGE OF SAMPLES

Each participant will be assigned a unique identifying number during the enrolment process, according to the Standard Operating Protocol in respect of participant identification for the study. The participant number will be linked to a pre-generated sample barcode for every clinical sample taken, which can be scanned at the testing laboratory.

Samples will be sent to the receiving laboratory at the Virus Reference Division, PHE Colindale by Royal Mail using approved packaging which will be supplied to each family. A brief paper form will be completed by parents to confirm date of sampling. All samples will be logged locally, to enable the identification of any lost or delayed samples and provide a log of where samples are currently stored.

Samples arriving at the receiving laboratory at the Virus Reference Division, PHE Colindale without accompanying paperwork will be initially processed (given that consent has already been obtained) but any results embargoed until confirmatory paperwork has been received from the family.

Samples will be initially processed from the administrative perspective and stored until formal processing in batches. Not all swabs received will undergo viral detection and quantification: swabs will be selected from representative cohorts of individuals, by previous

influenza vaccination status: no previous vaccination, previous LAIV only, previous injected influenza vaccine only. This will allow an assessment of the impact of previous LAIV receipt on viral shedding, something necessary to determine the effect of prior influenza immunisation on viral shedding. Any swabs not included in the viral quantification will be handled as per section 8.4.3.

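### The respiratory SAE window is tied to the visit-1 dose, so no respiratory collection window or scheduled contact is stated after a second LAIV dose

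*Combined protocol and SAP*

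**What the plan says.** Two consecutive sentences at the end of section 7.1 limit which serious events are collected for this study. SARs and SAEs unrelated to asthma or wheeze "will only be collected where onset is within 72 hours of vaccine administration", and no dose or visit is named. The next sentence deals with the rest and does name a visit: "Those relating to respiratory symptoms will be collected up to one month after LAIV at visit 1".

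Under section 6.1.2, children under 9 who are in a listed clinical risk category and have had no seasonal influenza vaccine "will be offered a second dose of LAIV at least 4 weeks later". The synopsis says that such children "will be eligible for a second dose 4 weeks later, as per DoH guidelines". One of the Table 1 risk categories is "Asthma requiring continuous or repeated use of inhaled or systemic steroids". No number of second doses is given: "We expect very few children to meet this criteria, as most would have received prior influenza vaccination". Section 6.1.2 adds that second-visit data go on their own CRF and stay out of the primary analysis. It does not describe that CRF's content or follow-up period.

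The schedule in section 6 places the second dose in the final column, alongside the 4-week follow-up. Nothing comes after it.

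**The concern.** Asthma deterioration after LAIV is the study's main safety question (sections 1.2 and 2.1). The protocol provides for some children to receive a second live-vaccine dose, yet the only stated period for collecting serious respiratory events starts at the first. The rule for non-respiratory events, in the sentence before, has no such restriction. Any asymmetry would be expected to run the other way.

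What is at stake is safety oversight rather than the primary estimate. Section 7.1.1 sends SAEs and SARs to the IDMC. Section 8.6 puts the study on hold for a single asthma or allergic episode needing intensive care and mechanical ventilation, for any death, or for similar or repeated SUSARs. Those triggers apply whichever dose came before. For the weeks after a second dose, they would operate without a defined respiratory collection window or a planned contact to feed them.

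**Working it through.** There is no plan figure to reproduce. The check is date arithmetic, followed by a comparison of the sections.

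**Inputs**
- W, length of the visit-1 respiratory window: one month (7.1), taken as 28 to 31 days.
- D, day of the second dose counted from the first: 28 or later (6.1.2). The synopsis gives 4 weeks, that is, day 28.

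**Overlap of the visit-1 window with the time after dose 2** = max(0, W − D)
- W = 28, D = 28: 28 − 28 = 0 days.
- W = 31, D = 28: 31 − 28 = 3 days, the most possible. As a share of a full one-month window, 3/31 = 9.7%, or about 10%.
- D of 31 or later: 0 days for any W.

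Three days is 72 hours. So the visit-1 respiratory window spans the first 72 hours after dose 2 only when that dose is given on the earliest possible day and the month is counted as 31 days. In every other case respiratory events have shorter cover than non-respiratory ones, or none.

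**Could another section close the gap?**
1. *7.1.1 and 7.3* require all adverse events to be recorded throughout the study and reported. These are general duties, whereas the end of 7.1 is an explicit study-specific limit. The sections conflict, and a site cannot tell which governs.
2. *6.1.2* provides a separate CRF, with no stated follow-up period.
3. *8.2* describes a call at least 72 hours after LAIV and within 7 days. It could be read as applying to each dose, although the schedule shows it only after visit 1. Even on the wider reading it stops at 7 days, not one month.
4. *7.1*, on following an adverse event until resolution or 30 days after the participant leaves the study, concerns events already known. It does not open a window for new ones.
5. *7.1.1* starts the 24-hour SAE clock when the site becomes aware. Without a scheduled contact, awareness of an admission elsewhere depends on the family or another hospital volunteering it.

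**Scale.** The documents give no count. For orientation only, each 1% of the 840 target would be 0.01 × 840 = 8.4 children, before allowing for families who decline the offer. Nothing in the documents supports a particular percentage.

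**The case against.** The strongest reply is that the documents do not establish non-collection. Section 6.1.2 provides a CRF for second visits. Section 7.1 defines adverse reactions in relation to any dose. Sections 7.1.1 and 7.3 call for every adverse event to be recorded and reported, and IDMC and SUSAR reporting carry no visit-1 limit. This stands. A reader might infer that respiratory SAEs after dose 2 are not collected and would never reach the IDMC; the text does not support that. What remains is a conflict between a specific limit and general duties, with no planned contact to make the general duties work.

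A reader might also infer that these children are at special risk because they have never met the vaccine. That does not fit the dose in question. By dose 2 they have had dose 1 under the protocol, with the 72-hour call, the 4-week questionnaire and the one-month respiratory window.

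Nor is the expectation of very few second doses contradicted elsewhere. Its stated reason is prior vaccination, not rarity of the Table 1 categories, so broad asthma eligibility does not undercut it. The swab cohorts in 8.4.2 ("no previous vaccination, previous LAIV only, previous injected influenza vaccine only") imply that some unvaccinated children are expected, but no cohort size is given and they are not restricted to under-9s. Section 6.1.2 reports that no child in SNIFFLE 1 would have needed a second dose, and section 6.2 that many SNIFFLE-1 families declined to return for vaccination at a separate visit. SNIFFLE-1 enrolled children with egg allergy (1.1), so it is an imperfect guide, but it does not point to a large number.

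Finally, the second dose is a duty-of-care provision outside the primary analysis. That is true, and it limits the analytical impact. It does not remove the need to collect serious events after a dose given under the protocol.

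**Conclusion.** The point holds as a gap and an internal conflict in safety collection. The respiratory SAE/SAR window is defined only from the visit-1 dose. It covers 0 to 3 days after a second dose at best, and no contact is scheduled afterwards. Read literally, the rule may leave out a respiratory SAE in the same hours in which a non-respiratory one is collected.

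This rests on taking one month as 28 to 31 days and the second dose as day 28 or later. It does not depend on how many second doses are given. That number is unstated and expected to be small, so the number of events that might be missed cannot be estimated. The primary outcome and its analysis are untouched. The correction is still worth making, because it concerns the study's main safety question and costs little.

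**What to change.** Reword the last sentence of section 7.1 so that serious respiratory events are collected for up to one month after each LAIV dose given under this protocol. Then reconcile it with the schedule in section 6, with 6.1.2, with the duties in 7.1.1 and 7.3, and with the hold triggers in 8.6. State what the second-visit CRF records and for how long. Make the Appendix 5 contact at 72 hours and the Appendix 6 contact at 4 weeks after dose 2 as well. Report these data separately and keep them out of the primary analysis, as already planned.

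The change affects data collection only; eligibility and dosing stay as they are. The cost is two calls of 2-3 minutes each, so 4 to 6 minutes per second-dose child, plus minor edits to the schedule and CRF. If second doses are as few as expected, the total burden is very small.

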**6 STUDY VISITS, PROCEDURES SCHEDULE and Patient Flow Diagram**

The study schedule is summarised in the following flow chart and table:

	Visit 1	24 hours later	72 hours later	6-7 days later	Follow-up 4 weeks later
Written Informed Consent (parent/ guardian)	X				
Written assent (child)	X				
Medical assessment	X				
Asthma control/symptom questionnaire: 
 
• Age 2-4 years: TRACK score (Appendix 1)
 
• Age 5-11 years: C-ACT score (Appendix 2a)
 
• Age 12+ years: ACT score (Appendix 2b)
 
	X				X
Vaccine administration followed by 20 mins observation	X				
Nasal swab at home		X	X	X	
Delayed effects telephone questionnaire at 72hrs			X		
Asthma assessment 4 weeks post LAIV					X
2 nd dose in children <9 years who meet DoH criteria (see 6.1.2)					X

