## 8.2 TELEPHONE FOLLOW UP

Participants' families will be contacted by the local research team at least 72 hours after LAIV administration (and within 7 days, to allow for weekends), to determine whether their child has experienced any delayed symptoms which might be attributable to the vaccine. This telephone consultation will take approximately 2 minutes. A guide for this telephone call is provided in Appendix 5. These data will be recorded on the CRF. Following this, the CRF will be deemed complete and forwarded to the coordinating centre.

If after three attempts (on three separate days) the local study team is unable to contact the family, the child will be deemed lost to follow up and this will be documented on the CRF, which will then be closed.

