**Guide to telephone interview:**

1. Confirm interviewee's identity

2. Introduce yourself:

*"I am <name>, from the SNIFFLE-4 Study. We arranged to speak briefly today to find how <participant's name> is going after his/her 'flu vaccine on <date>"*

3. *"Have you noticed any health problems since the vaccine?"*

4. For each symptom reported:

- *When did this start?*
- *How long did this last?*
- *Did you do anything as a result?*

5. *"Since the vaccine,*

- i. Have you needed to give your child more reliever medicine (e.g. ventolin) than normal?*
- ii. Have you had to take <participant's name> to see a Doctor because of his/her breathing?*
- iii. (If YES) – did you have to take them to hospital?*
- iv. (If YES) – did <participant's name> have to stay in hospital overnight?*
- v. Did <participant's name> have to start any medicines, like an oral steroid? If so, for how long?*

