**Guide to telephone interview:**

1. Confirm interviewee's identity

2. Introduce yourself:

*"I am <name> from the SNIFFLE-4 Study. Your child <participant's name> had the 'flu vaccine with us one month ago, and we arranged to speak to find out if you had needed to do anything different with his asthma/wheezing"*

3. Complete appropriate TRACK / C-ACT / ACT Questionnaire over the telephone

(see separate questionnaires)

4. Finally, ask the following questions:

*Since the vaccine,*

*i) Have you had to take <participant's name> to see a Doctor because of his/her breathing?*

*ii) (If YES) – did you have to take them to hospital?*

*iii) (If YES) – did <participant's name> have to stay in hospital overnight?*

*iv) Did <participant's name> have to start any medicines, like an oral steroid? If so, for how long?*

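### Respiratory SAE collection is tied to the visit 1 dose, so no active collection is set for most of the month after a second dose of LAIV

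*Combined protocol and SAP*

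**What the plan says.** Section 7.1 (Definitions) sets two collection windows for serious adverse events and reactions. For events not related to asthma or wheeze, they "will only be collected where onset is within 72 hours of vaccine administration", and no visit is named. For respiratory events the wording is different: "Those relating to respiratory symptoms will be collected up to one month after LAIV at visit 1".

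Section 6.1.2 provides for a second dose. Children under 9 who are in a clinical risk category and have had no previous seasonal influenza vaccine "will be offered a second dose of LAIV at least 4 weeks later". The protocol expects very few such children and gives duty of care as the reason for the provision. On the data it says: "Data pertaining to second visits will be collected on a separate CRF, but not used in the primary analysis". That CRF is not among the documents.

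The section 6 schedule puts the second dose ("dose in children <9 years who meet DoH criteria (see 6.1.2") in its last column, the 4-week follow-up. There is no later column.

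Section 8.2 describes a telephone call "at least 72 hours after LAIV administration (and within 7 days, to allow for weekends". The wording is general and does not say whether it applies after each dose. The Appendix 5 guide for that call asks about breathing, for example "Have you needed to give your child more reliever medicine (e.g. ventolin) than normal", and about doctor and hospital visits and oral steroids. The 4-week contact (section 8.1.3 and Appendix 6) is described once, with no repeat after a second dose.

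**The concern.** Worsening of asthma or wheeze in the 4 weeks after LAIV is the harm this study is designed to look for (sections 2.1 and 2.2). After the first dose, serious respiratory events are collected for about a month. After a second dose, given under the same protocol to children under 9, the stated window has closed or is about to close.

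An asthma admission 10 days after the second dose illustrates what is at stake. It would fall outside the section 7.1 window and after the 72-hour call, and no scheduled contact would ask about it. Section 1.1 puts nasal shedding of vaccine virus at 7 to 10 days, more prominent in younger children, so the last possible contact may come before shedding ends. The hold rule in section 8.6 for an asthma episode needing ICU admission and ventilation names no dose, and it works only if the study team learns of the event.

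**Working it through.** The plan gives no figure to reproduce. The check is a reading of the sections together, with a count of days.

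**Inputs**
- Respiratory window: one month from the visit 1 dose (section 7.1). The protocol does not define a month, so I take 28 to 31 days as an assumption.
- Second dose: day 28 after visit 1 at the earliest (section 6.1.2).
- Telephone call: day 3 to day 7 after LAIV (section 8.2).
- Contacts scheduled after the second-dose visit: none (section 6).

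**Step 1. What is left of the stated window when the second dose is given.** Days left = max(0, length of month − day of second dose).
- Month of 31 days, second dose on day 28: 31 − 28 = 3 days.
- Month of 28 days, second dose on day 28: 28 − 28 = 0 days.
- Second dose on day 31 or later: 0 days.

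So at most about 3 days remain.

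**Step 2. Gap if the 72-hour call also follows the second dose.** This is the reading more favourable to the protocol. The call can pick up respiratory events up to the day it is made.
- Smallest gap: 28 − 7 = 21 days.
- Largest gap: 31 − 3 = 28 days.

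**Step 3. Gap if the call applies only after visit 1, as the schedule shows it.** Only the remainder from step 1 counts.
- With 3 days left of a 31-day month: 31 − 3 = 28 days.
- With nothing left: the whole month, 28 to 31 days.

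**Step 4. Does another active step fill the gap?** The 4-week contact does not. Appendix 6 is built around one vaccination a month earlier ("we arranged to speak to find out if you had needed to do anything different with his asthma/wheezing"), and no repeat is scheduled. Under section 8.2 the CRF is treated as complete once the 72-hour call has been made. The 30-day provision in section 7.1 is about following up an event already known; it does not look for new ones.

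**Step 5. Is there a passive route?** Yes. Section 7.1.1 has the investigator record all adverse events throughout the study, section 7.3 says that all should be reported, and SAE reporting under 7.1.1 and 7.3.2 starts when the site becomes aware. None of these carries a visit 1 limit. They conflict with the limit in section 7.1, which is stated as a rule for this study in particular, and the documents do not say which prevails.

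**The case against.** The best defence is that the limit is deliberate. The synopsis defines the intervention as one dose and allows a second only as a duty of care under national guidance. The objectives compare symptoms before and 4 weeks after LAIV and do not promise a second 4-week period. The vaccine is part of the routine programme. On this view, naming visit 1 limits collection to the dose under study. That is a plausible account of why the text reads as it does. But the second dose is given within the protocol, its data are to be recorded, and keeping it out of the primary analysis is no reason to stop looking for serious respiratory events after it.

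A reader might also infer that an event in the gap could not reach the record at all. The documents do not support that. The general recording and reporting duties have no visit 1 limit, section 7.1 defines adverse reactions by reference to any dose, and the section 8.6 hold rules name no dose. Recruits are under the care of participating sites (section 4.1), so a site could well hear of an admission. What stands is narrower: these routes depend on the site happening to learn of the event, and the section 7.1 limit makes it unclear whether the event would then be collected.

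Nor can one infer that follow-up after the second dose is absent in practice. The second-visit CRF may provide for it, but its content is unknown. The point is about what the protocol text sets.

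**Conclusion.** The point holds as a minor safety gap. As written, section 7.1 leaves at most about 3 days of respiratory SAE collection after a second dose. If the 72-hour call is granted, no active collection is set from about day 3 to 7 until one month after that dose, or about 21 to 28 days. If it is not granted, the gap is about 28 to 31 days. One month after the second dose is the period that matches the cover given after the first; the protocol itself sets no such period for the second dose.

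The conclusion rests on taking a month as 28 to 31 days, on the second dose being given on day 28 or later, and on the protocol text alone. The number of children is not given and cannot be estimated from the documents; the protocol expects very few. A reader might infer some effect on the main result, but there is none, because second-visit data are kept out of the primary analysis. What is affected is the completeness of serious respiratory safety data for these children.

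**What to change.** Two changes:
1. In section 7.1, make the respiratory window run up to one month after each dose of LAIV, in place of the reference to visit 1.
2. For children given a second dose, add to the section 6 schedule the 72-hour call and one 4-week telephone or online contact. The 4-week contact can use question 4 (i to iv) of Appendix 6, asked about the time since the second dose.

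The cost is a minor amendment, small updates to the second-visit CRF and probably to the information leaflets and consent forms (the amendment history shows these being revised when the swabbing procedure changed), and about four more weeks of follow-up for very few children. The contacts take about 2 minutes for the 72-hour call, if it is not already being made, and 2 to 3 minutes at 4 weeks. No extra hospital visit is needed.
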